2.9 Pharmacokinetic endpoints

The PK set will be used for all PK analyses.

Artemether, DHA and lumefantrine plasma concentration, C_{max} and AUC data (as applicable) will be listed by cohort, treatment group, subject, and visit/sampling time point.

Descriptive summary statistics will be provided by cohort, treatment group, and visit/sampling time point, including the frequency (n, %) of concentrations below the lower limit of quantification (LLOQ). Summary statistics will include mean (arithmetic and geometric), SD, CV (arithmetic and geometric), median, minimum, and maximum. PK concentrations below the LLOQ will be treated as zero in summary statistics and for the calculation of pharmacokinetic parameters by non-compartmental analysis. A geometric mean will be calculated using half LLOQ value for concentrations below LLOQ. CV for arithmetic mean will be computed as $mean/SD \times 100$. CV for geometric mean will be computed as $\sqrt{e^{var(\log transformed data)}} - 1 \times 100$.

For DHA C_{max} and Lumefantrine C_{max} (LUM C_{max}) the 90% 2-sided confidence intervals for the geometric mean will be calculated on the natural log scale and then anti-log transformed back to the original scale for the following comparisons:

- DHA C_{max} vs. historical data (Table 5-7)
- Lumefantrine C_{max} vs. historical data (Table 5-7)

DHA C_{max} and lumefantrine C_{max} are considered to be comparable with historical data if the 90% confidence interval contains the Historical values. The analysis of ART C_{max} is described in [Section 2.5](#), the analysis of LUM C_{168h} in [Section 2.6](#).

Non-compartmental PK will be used to calculate the pharmacokinetic parameters wherever possible. Due to the limited number of samples collected in this study, a naive pool approach for data analysis may also be followed for reporting PK parameters such as ART C_{max} /other C_{max} and AUC, if feasible.

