| Figure 16-2 | Reference ranges for head circumference in males (0-2 years) | 71 |
| Figure 16-3 | Reference ranges for head circumference in females (0-13 weeks) | 72 |
| Figure 16-4 | Reference ranges for head circumference in females (0-2 years) | 73 |

List of abbreviations

| | |
|------------------|--|
| ACPR | Adequate Clinical and parasitological Response |
| ACT | artemisinin-based combination therapy |
| AE | adverse event |
| ALP | alkaline phosphatase |
| ALT | alanine aminotransferase |
| ART | artemether |
| ARV | antiretroviral |
| ASAQ | artesunate-amodiaquine |
| AST | aspartate aminotransferase |
| ATC | Anatomical Therapeutic Chemical |
| AUC | Area Under the Curve |
| b.i.d. | twice a day |
| BMI | Body Mass Index |
| BW | body weight |
| CFR | Code of Federal Regulation |
| CI | Confidence Interval |
| C _{max} | in the context of this study, C _{max} is meant as the higher concentration between those at 1 hour or 2 hours post first dose |
| CMO | Chief Medical Office (Novartis) |
| CNS | Central Nervous System |
| CRF | Case Report/Record Form (paper or electronic) |
| CRO | Contract Research Organization |
| CTT | Clinical Trial Team |
| CV | coefficient of variation |
| DBP | Diastolic Blood Pressure |
| DHA | Dihydroartemisinin |
| DMC | Data Monitoring Committee |
| e.g. | For example |
| EC | Ethics committee |
| eCRF | Electronic Case Report Form |
| EDC | Electronic Data Capture |
| EMA | European Medicines Agency |
| ETF | Early Treatment Failure |
| FAS | full analysis set |
| FCT | Fever clearance Time |
| FDA | Food and Drug Administration |
| GCP | Good Clinical Practice |
| GGT | Gamma-glutamyl transferase |
| GLDH | Glutamate dehydrogenase |
| HIV | Human Immunodeficiency Virus |
| i.e. | That is to say |

| | |
|-----------------|--|
| IB | Investigator's Brochure |
| ICH | International Conference on Harmonization of Technical Requirements for Registration of Pharmaceuticals for Human Use |
| IEC | Independent Ethics Committee |
| IMCI | Integrated Management of Childhood Illness |
| IN | Investigator Notification |
| INR | International normalized ratio of prothrombin time of blood coagulation |
| IRB | Institutional Review Board |
| IRT | Interactive Response Technology |
| LAR | Legally Acceptable Representative |
| LCF | Late Clinical Failure |
| LLOQ | lower limit of quantification |
| LPF | Late Parasitological Failure |
| MedDRA | Medical dictionary for regulatory activities |

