2.1 Data analysis general information

Data will be analyzed by [REDACTED] on behalf of Novartis after the final DBL using SAS version 9.4 according to the data analysis presented in Section 12 of the study protocol which will also be available in [Appendix 16.1.1 of the CSR](#). Important information is given in the following sections and details will be provided, as applicable, in [Appendix 16.1.9 of the CSR](#).

There will be two planned interim assessments, one after Cohort 1, the second one after Cohort 2. More details can be found in [Section 2.12](#).

Data analyses required for the interim assessments will also be analyzed by [REDACTED] and corresponding outputs will be provided to the DMC. Outputs for the DMC will be part of the CSR shell document. No separate SAP or TFL shell document will be prepared.

After the first 9 patients in Cohort 1 and the first 3 and 9 patients in the higher age subgroup of Cohort 2 (1-28 days) and after the first 3 patients in the 2 younger subgroups of Cohort 2 (if they are recruited) have been treated with the same dose and followed up for at least 2 weeks (and optionally once 9 patients from the age group 15-28 days have completed Day 15), the database will be cleaned reasonably, data management reports using the raw data will be used for the regular review meetings and PK summaries will be generated by Novartis PK scientist.

Statistical analyses will be performed by cohort and treatment group. If there are treatment groups that are used for multiple cohorts, descriptive statistics will be calculated for these treatment groups by pooling data from all cohorts for the primary and key secondary endpoints.

Unless otherwise stated, summary tables/figures/listings will be on all patients included in the population under consideration.

Categorical data will be summarized as frequencies and percentages. For continuous data mean, standard deviation, median, minimum, and maximum will be presented. For selected parameters, the 25th and 75th percentile will also be presented.

There is no stratification done in this study.

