3.1.1 Primary endpoint(s)

Artemether C_{max} (represents the higher concentration between the concentrations at 1 hour and 2 hours) after the first dose is the primary endpoint. The distribution of C_{max} is best described by log normal distribution. The half width of the 2-sided 90% confidence interval for log C_{max} is the target for sample size calculation. The relevant historical data for sample size calculation are the standard deviations of log C_{max} , which are usually invariant to the dosage (See [Table 3-1](#)).

Table 3-1 Standard deviation for log C_{max} in Coartem studies A2102 and B2306

Study and formulation of artemether-lumefantrine	Artemether C_{max}	Day 8 Lumefantrine concentration
A2102* (healthy volunteers) 80:480 mg tablet	0.58	-
A2102 (healthy volunteers) 4 tablets of 20:120 mg	0.52	-
B2306 (infants >28 days of age) 20:120 mg dispersible tablet	0.65	0.654

*Study CCOA566A2102; **Study CCOA566B2306

The table shows that the standard deviation for log C_{max} was about 12% to 25% higher for infants in Study B2306 than for healthy volunteers in Study A2102. The patient population in the current study (B2307) is similar to the patient population in Study B2306.

For log C_{max} , a standard deviation of 0.65 from Study B2306 will therefore be used. Based on the standard deviation of 0.65 in log scale, a sample size of 16 evaluable patients will provide 80% probability that the observed half width of 2-sided 90% CI for log C_{max} is ≤ 0.337 or 1.4 times (covering the targeted C_{max}) in terms of ratio (nQuery Advisor 8). This sample size is applied to each cohort.

PK sampling will be designed in order to get all patients evaluable for artemether C_{max} analysis. Taking into account about 10% of patients not evaluable for this PK analysis, about 18 patients should be enrolled in each cohort.

For each cohort the sample size will be increased slightly to allow for higher dropouts for the secondary endpoint, Day 8 (168 h) lumefantrine concentration (see [Section 3.1.2](#)).

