3.1.2 Secondary endpoint(s)

Power consideration for Day 8 (168 h) lumefantrine concentration

The Day 8 (168 h) lumefantrine concentration is the key secondary endpoint. The distribution of Day 8 lumefantrine concentration is best described by log normal distribution. In Study B2306, the standard deviation for the log concentration from 16 infants was 0.65. Based on the standard deviation of 0.65 in log scale, a sample size of 16 evaluable patients will provide 80% probability that the observed half width of 2-sided 90% CI for the log concentration is ≤ 0.337 or 1.4 times in terms of ratio (nQuery Advisor 8). This sample size is applied to each cohort.

The percentage of patients who are not evaluable for Day 8 lumefantrine concentration may be higher than that for artemether C_{max} which is based on the concentrations on Day 1. Taking into account about 25% of patients not evaluable for this PK analysis, about 22 patients will be enrolled in each cohort in order to achieve the number of patients evaluable for this analysis as specified above.

Power consideration for PK checking in each cohort

After about 9 patients have been enrolled in each cohort, PK checking will be performed to see if the dose level should be adjusted. Considering that about 10% of patients would be non-evaluable for artemether C_{max} , this will lead to about 8 patients evaluable for artemether C_{max} . The probability that the observed half width of 2-sided 90% CI in log scale is ≤ 0.693 or 2 in terms of ratio for artemether C_{max} is 96% if the standard deviation in log scale is same as the assumed 0.65 or 80% if the standard deviation in log scale is as high as 0.85 (nQuery Advisor 8). Additional optional PK checks can also be implemented.

Note:

The requirement for an evaluable number of patients is 16 for both the primary endpoint (artemether C_{max} (max concentration between concentrations at 1 hour and 2 hours)) and the secondary endpoint (Day 8 (168 h) lumefantrine concentration). An additional number of patients is included due to potential dropouts for each endpoint. In case that the number of dropouts is less than expected, the enrollment for a cohort may be stopped after at least 16 patients are deemed evaluable for PK analyses (C_{max} or Day 8 concentration).

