In order to support an early readout of the study based on observed PK, efficacy and safety, enrollment may be stopped. Thereafter, the criterion of 0.337 for the observed half width of 2-sided 90% CI for the log concentration will be increased to a threshold that is appropriate for the sample size.

Additional modeling and simulation may be performed to support the planned analyses.

4 Change to protocol specified analyses

No change from protocol specified analysis was made.

5 Appendix

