5.7 Statistical models

5.7.1 Primary analysis

The primary analysis is detailed in [Section 2.5](#).

The primary endpoint ART C_{max} will be displayed by cohort and treatment group using the geometric mean. The geometric mean will be calculated by deriving the mean of the log-transformed values followed by an exponential transformation, i.e. *Geometric Mean (GM) = e^{mean(log(x))}* with x = ART C_{max} of a participant.

Corresponding 2-sided 90% confidence intervals for the GM will be calculated assuming a log normal distribution of the primary endpoint. The lower and upper limits will be calculated as follows:

$$\exp(\bar{x} \pm t_{(1-\frac{\alpha}{2};n-1)} \times \frac{s}{\sqrt{n}})$$

with \bar{x} = the arithmetic mean of the log-transformed endpoint, $t_{(1-\frac{\alpha}{2};n-1)}$ = the $(1 - \frac{\alpha}{2})$ critical value of the Student's t statistic with $n - 1$ degrees of freedom, s = the standard deviation of the log-transformed endpoint, and n = the number of patients with available endpoint in the corresponding cohort and treatment group.

The logarithm to the natural base is used.

The calculation will be implemented in SAS using PROC MEANS on log data followed by an exponential transformation.

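### SAP 2.9 defines the arithmetic CV upside down (mean over SD), so the descriptive PK tables would report its reciprocal

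*SAP*

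**What the plan says.** SAP Section 2.9 lists the descriptive statistics for plasma concentrations and PK parameters, by cohort, treatment group and sampling time: "Summary statistics will include mean (arithmetic and geometric), SD, CV (arithmetic and geometric), median, minimum, and maximum". It then gives the arithmetic CV formula: "CV for arithmetic mean will be computed as $mean/SD", times 100. (The dollar sign is a typesetting mark, not part of the formula.)

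Protocol Section 12.5.3 asks for the same statistics but gives no CV formula. The protocol's abbreviation list expands CV as "coefficient of variation", and the SAP's list does the same. SAP Section 4 declares: "No change from protocol specified analysis was made".

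On the interim assessments, SAP Section 2.1 says: "Outputs for the DMC will be part of the CSR shell document. No separate SAP or TFL shell document will be prepared".

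**The concern.** A coefficient of variation expresses the SD as a percentage of the mean. The SAP has numerator and denominator exchanged. The result is not a rescaled CV. It falls as variability rises, so a comparison of groups or sampling times on that column would run backwards.

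The error could also escape notice, because values such as 97% or 138% are not implausible for PK data in this population. Since the interim outputs share the CSR shells and have no SAP of their own, any arithmetic CV shown to the DMC at an interim assessment would follow the same wording.

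**Working it through.** The documents report no arithmetic CV, so there is no stated figure to reproduce. The check applies both formulas to the plan's own variability figures.

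**1. From the log-scale SDs**

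Inputs:
- Log SD 0.65, from SAP 3.1.1: "a standard deviation of 0.65 from Study B2306 will therefore be used".
- Log SD 0.85, the stress value in SAP 3.1.2: "80% if the standard deviation in log scale is as high as 0.85".
- Log-normality, which the SAP assumes for the primary endpoint in Section 5.7.1: "Corresponding 2-sided 90% confidence intervals for the GM will be calculated assuming a log normal distribution of the primary endpoint".

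For a log-normal variable with log SD *s*, the arithmetic CV is SD/mean = √(exp(*s*²) − 1). The SAP formula returns 1 divided by that.

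| Log SD *s* | *s*² | Correct CV | SAP formula |
|---|---|---|---|
| 0.65 | 0.4225 | √(exp(0.4225) − 1) = 0.725, i.e. 72.5% | 1/0.725 = 1.379, i.e. 137.9% |
| 0.85 | 0.7225 | √(exp(0.7225) − 1) = 1.029, i.e. 102.9% | 1/1.029 = 0.971, i.e. 97.1% |

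The more variable case receives the lower reported CV.

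**2. From the historical artemether Cmax values in protocol Table 4-1**

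The table does not label the ± figure. It is read here as an SD, which is an assumption.

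| Group | Mean ± SD (ng/mL) | Correct: SD/mean × 100 | SAP: mean/SD × 100 |
|---|---|---|---|
| B2306, <5 kg | 509 ± 309 | 60.7% | 164.7% |
| B2303, 5 to <15 kg | 196 ± 204 | 104.1% | 96.1% |
| B2303, 15 to <25 kg | 150 ± 106 | 70.7% | 141.5% |
| B2303, 25 to <35 kg | 134 ± 56.7 | 42.3% | 236.3% |

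As ratios, the last two columns multiply to 1 in every row, so they agree only when SD equals the mean. The ordering is exactly reversed: the least variable group (25 to <35 kg) gets the largest value and the most variable (5 to <15 kg) gets the smallest.

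**3. Sampling times with many values below the LLOQ**

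SAP 2.9 sets such values to zero in summary statistics. As a hypothetical, suppose 1 of 16 patients has a quantifiable concentration *c* and the other 15 are zero. The mean is *c*/16. The sample variance is (*c*² − *c*²/16)/15 = *c*²/16, so the SD is *c*/4. The correct CV is (1/4)/(1/16) = 4, or 400%. The SAP formula gives 25%.

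**4. What depends on this CV**

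- Primary and key secondary analyses (SAP 2.5, 2.6, 5.7): geometric means with t-based 90% intervals on the log scale. Not affected.
- DHA and lumefantrine Cmax against historical data (SAP 2.9): the same method. Not affected.
- Sample size and PK-check precision (SAP 3.1.1, 3.1.2): SDs of log values. Not affected.
- Stated PK-check criteria (protocol 12.5.3): concentrations and Cmax against historical ranges. Not affected.
- Descriptive PK tables (SAP 2.9): affected in the arithmetic CV column.

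**The case against.** The strongest reply is that this is a slip of the pen. Both abbreviation lists say coefficient of variation, the protocol requires that statistic, and the SAP declares no departure from the protocol. A competent programmer would compute SD/mean, and 236% beside a mean of 134 and an SD of 56.7 would be caught in table review. No decision rests on the column, and the mean and SD stand next to it. For the 5 to <15 kg group, the main historical comparator, the two formulas differ only modestly (104.1% against 96.1%). The 0.85 is a stress value, not an expected one, and the log-normal conversion suits Cmax better than concentrations at times with many values below the LLOQ. Finally, the PK summaries for the 3- and 9-patient checks come from the sponsor's PK scientist and are not tied to the CSR shells, and no passage says that an arithmetic CV is shown to the DMC.

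Most of this stands as a limit on the consequences. The intent is clear, the harm is descriptive, and the DMC link is conditional and confined to the interim assessments.

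It does not remove the error. The SAP sentence is the only operative formula. A program that follows it produces wrong tables, and one that ignores it departs from the plan without a record. The modest gap in the 5 to <15 kg row arises because SD and mean happen to be close there. Table review may catch the extreme values but would probably miss those near 100%.

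**Conclusion.** The formula is wrong as written and should be corrected. The arithmetic CV in SAP 2.9 is the reciprocal of the coefficient of variation. At the planning log SD of 0.65 it would report 137.9% instead of 72.5%, and it reverses the ranking of variability between groups and sampling times.

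That the formula is inverted rests on no assumption. The sizes rest on log-normality (first illustration) and on reading ± as SD in Table 4-1 (second). Wrong tables would result only if the programs follow the text, which the documents cannot show. No endpoint conclusion, stated dose-check criterion or sample size figure changes.

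**What to change.** In SAP Section 2.9, replace the arithmetic CV formula with: CV for arithmetic mean = SD/mean × 100.

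Then check the PK table programs, and any interim outputs already produced, to see which formula was used. Outputs from interim assessment 1 may well exist: the plan places it before Cohort 2, and the rationale for protocol Amendment 1 records that Cohort 2 recruitment was under way.

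While that sentence is open, confirm in the original PDF that the geometric CV beside it reads √(exp(variance of the log-transformed data) − 1) × 100, with the −1 under the root. The extracted text leaves this unclear, possibly through extraction alone, and no error is claimed there. For a log SD of 0.65, the intended form gives 72.5%. With the −1 outside the root and the difference multiplied by 100, it would give 23.5%.

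The cost is one line of SAP text and a short program check. The design, sample size and endpoint analyses are unchanged.

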2.10 PD and PK/PD analyses

A PK/PD analysis may be attempted based on available historical information. Due to the small sample size in this study, detailed PK/PD assessment based on this study alone may be of limited value.

This analysis will be reported outside of the CSR.

2.12 Interim analysis

Interim assessment 1

Interim assessment 1 will be done after all patients in Cohort 1 have completed the core period (Day 43). Artemether, DHA, and lumefantrine concentrations, PK parameters, key efficacy and safety endpoints will be analyzed by the study biostatistics team. These results will be reviewed by Novartis Clinical team and the DMC to reach a decision about progression to Cohort 2 and the starting dose level in that Cohort.

Interim assessment 2

Interim assessment 2 will be done after all patients in Cohort 2 have completed the core period (Day 43). For this interim assessment all data up to Day 43 will be cleaned and included. Efficacy and safety parameters and PK exposure data from both cohorts will be assessed.

Additional interim assessments may be conducted to support decision making based on early read-out of study data.

Additional ad-hoc safety reviews may be requested by the DMC or Novartis if needed (e.g. in case of SAEs).

3 Sample size calculation

The sample size is calculated and justified based on the precision of estimating artemether C_{max} (primary endpoint) and Day 8 (168 h) lumefantrine concentration (secondary endpoint) separately for Cohort 1 and Cohort 2.

3.1.1 Primary endpoint(s)

Artemether C_{max} (represents the higher concentration between the concentrations at 1 hour and 2 hours) after the first dose is the primary endpoint. The distribution of C_{max} is best described by log normal distribution. The half width of the 2-sided 90% confidence interval for log C_{max} is the target for sample size calculation. The relevant historical data for sample size calculation are the standard deviations of log C_{max} , which are usually invariant to the dosage (See [Table 3-1](#)).

Table 3-1 Standard deviation for log C_{max} in Coartem studies A2102 and B2306

Study and formulation of artemether-lumefantrine	Artemether C_{max}	Day 8 Lumefantrine concentration
A2102* (healthy volunteers) 80:480 mg tablet	0.58	-
A2102 (healthy volunteers) 4 tablets of 20:120 mg	0.52	-
B2306 (infants >28 days of age) 20:120 mg dispersible tablet	0.65	0.654

*Study CCOA566A2102; **Study CCOA566B2306

The table shows that the standard deviation for log C_{max} was about 12% to 25% higher for infants in Study B2306 than for healthy volunteers in Study A2102. The patient population in the current study (B2307) is similar to the patient population in Study B2306.

For log C_{max} , a standard deviation of 0.65 from Study B2306 will therefore be used. Based on the standard deviation of 0.65 in log scale, a sample size of 16 evaluable patients will provide 80% probability that the observed half width of 2-sided 90% CI for log C_{max} is ≤ 0.337 or 1.4 times (covering the targeted C_{max}) in terms of ratio (nQuery Advisor 8). This sample size is applied to each cohort.

PK sampling will be designed in order to get all patients evaluable for artemether C_{max} analysis. Taking into account about 10% of patients not evaluable for this PK analysis, about 18 patients should be enrolled in each cohort.

For each cohort the sample size will be increased slightly to allow for higher dropouts for the secondary endpoint, Day 8 (168 h) lumefantrine concentration (see [Section 3.1.2](#)).

3.1.2 Secondary endpoint(s)

Power consideration for Day 8 (168 h) lumefantrine concentration

The Day 8 (168 h) lumefantrine concentration is the key secondary endpoint. The distribution of Day 8 lumefantrine concentration is best described by log normal distribution. In Study B2306, the standard deviation for the log concentration from 16 infants was 0.65. Based on the standard deviation of 0.65 in log scale, a sample size of 16 evaluable patients will provide 80% probability that the observed half width of 2-sided 90% CI for the log concentration is ≤ 0.337 or 1.4 times in terms of ratio (nQuery Advisor 8). This sample size is applied to each cohort.

The percentage of patients who are not evaluable for Day 8 lumefantrine concentration may be higher than that for artemether C_{max} which is based on the concentrations on Day 1. Taking into account about 25% of patients not evaluable for this PK analysis, about 22 patients will be enrolled in each cohort in order to achieve the number of patients evaluable for this analysis as specified above.

Power consideration for PK checking in each cohort

After about 9 patients have been enrolled in each cohort, PK checking will be performed to see if the dose level should be adjusted. Considering that about 10% of patients would be non-evaluable for artemether C_{max} , this will lead to about 8 patients evaluable for artemether C_{max} . The probability that the observed half width of 2-sided 90% CI in log scale is ≤ 0.693 or 2 in terms of ratio for artemether C_{max} is 96% if the standard deviation in log scale is same as the assumed 0.65 or 80% if the standard deviation in log scale is as high as 0.85 (nQuery Advisor 8). Additional optional PK checks can also be implemented.

Note:

The requirement for an evaluable number of patients is 16 for both the primary endpoint (artemether C_{max} (max concentration between concentrations at 1 hour and 2 hours)) and the secondary endpoint (Day 8 (168 h) lumefantrine concentration). An additional number of patients is included due to potential dropouts for each endpoint. In case that the number of dropouts is less than expected, the enrollment for a cohort may be stopped after at least 16 patients are deemed evaluable for PK analyses (C_{max} or Day 8 concentration).

In order to support an early readout of the study based on observed PK, efficacy and safety, enrollment may be stopped. Thereafter, the criterion of 0.337 for the observed half width of 2-sided 90% CI for the log concentration will be increased to a threshold that is appropriate for the sample size.

Additional modeling and simulation may be performed to support the planned analyses.

4 Change to protocol specified analyses

No change from protocol specified analysis was made.

5 Appendix

